### 10.6.3 Monitoring related to two consecutive LDL-C <25 mg/dL (0.65 mmol/L)

Patients who achieve 2 consecutive LDL-C levels <25 mg/dL (0.65 mmol/L) during the study will be monitored and managed as per [Appendix A](#) (any time after randomization) as the lower limit of safe and effective LDL-C lowering has not yet been established. An independent external physician(s) (also known as independent physician) will be notified by the central laboratory of 2 consecutive LDL-C <25 mg/dL (0.65 mmol/L). The independent physician will review the unmasked LDL-C values and patient safety data, in close collaboration with the dedicated member of the Phase 3a DMC (implemented for all Phase 3 studies evaluating the efficacy and safety of alirocumab on LDL-C). This dedicated Phase 3a DMC member will then transmit any information as necessary to the common member involved in both DMCs (CV DMC and Phase 3a DMC).

Please see [Appendix A](#) for an outline of the process.

Then at subsequent visits, specific actions can be undertaken depending on the alirocumab dose (down-titration or discontinuation) as follows:

- On dose of 150 mg Q2W: if LDL-C <25 mg/dL (including LDL-C <15 mg/dL) on 2 consecutive values, down-titration to 75 mg Q2W will be done in a blinded manner at the next visit. The patient will remain at the down titrated dose of 75 mg Q2W for the remaining duration of the study, unless patient meets criteria below. As described above, specific monitoring consisting of review of patient level listing will be implemented.
- On dose of 75 mg Q2W:
  - If LDL-C <25 mg/dL on 2 consecutive values but there are no 2 consecutive measurements < 15 mg/dL (i.e. no measurement < 15 mg/dL or only one occasional measurement < 15 mg/dL): study treatment with 75 mg Q2W will be continued but additional monitoring with review of individual patient profiles will be implemented, to further confirm the safety of low LDL-C levels. A site alert related to 2 consecutive LDL-C < 25 mg/dL (0.65 mmol/L) may be requested by the independent physician (after consultation with dedicated phase 3a DMC member)
  - If measured LDL-C <15 mg/dL on 2 consecutive measurements: study treatment with 75 mg Q2W will be discontinued at the next visit. In order to maintain the blind there will be blinded substitution to placebo injections for the remaining duration of the study

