Subgroup of patients with 2 consecutive LDL-C <25 mg/dL (<0.65 mmol/L)

A 2-step approach will be used to analyze the safety in relation to low LDL-C.

The first step will screen events for potential signal using 2 approaches. The first approach will be a direct comparison of patients with 2 consecutive LDL-C <25 mg/dL versus \geq 25 mg/dL (ie, patients without 2 consecutive LDL-C <25 mg/dL) within the alirocumab treatment group. Since these 2 groups are based on post-randomization data with a potential for bias, a second approach will compare the alirocumab effect versus placebo according to categories based on baseline LDL-C. The frequency of patients with 2 consecutive LDL-C <25 mg/dL is expected to be the largest in the category with the lowest baseline LDL-C and be lower and lower in the categories with higher baseline LDL-C. Therefore, an event induced by low LDL-C should be associated with a higher alirocumab effect versus placebo (ie, higher HR) in the first baseline LDL-C category(ies) than in the subsequent categories. Details of these 2 approaches are provided below.

The second step will consist in the comparison of patients with 2 consecutive LDL-C <25 mg/dL versus \geq 25 mg/dL within the alirocumab group for the events detected in the first step, as well as for pre-specified events.

Similar analyses will be provided considering 15 mg/dL (0.39 mmol/L) as threshold instead of 25 mg/dL.

First step

First screening approach

TEAE summary by primary SOC, HLGT, HLT, and PT as well as groupings of events (ie, cataract, neurological events, neurocognitive disorders and "new onset of diabetes" [see Section 3.4.5.3 for the definition]) will be provided on the safety population in the groups below:

- Placebo group
- Alirocumab group
- Alirocumab LDL-C \geq 25 mg/dL (ie, alirocumab patients without 2 consecutive LDL-C <25 mg/dL)
- Alirocumab patients with 2 consecutive LDL-C <25 mg/dL

For patients with 2 consecutive LDL-C <25 mg/dL, analyses will be done on the period starting from the first of the 2 consecutive LDL-C lower than 25 mg/dL to the upper limit of the TEAE period excepted for patients down-titrated from 150 mg to 75 mg for whom the analysis period will end at the date of last injection of 150 mg +70 days (as patients down-titrated from 150 mg to 75 mg are likely to come back above 25 mg/dL).

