The time to the first TEAE/event will be compared for patients with 2 consecutive LDL-C <25 mg/dL versus $\geq 25 \text{ mg/dL}$, within the alirocumab group, using a Cox model, including the covariate for 2 consecutive LDL C <25 mg/dL (Yes/No). Hazard ratio (and 95% CI) from this model will be provided. The event rate per 100 patient-years (the number of patients with an event in question divided by total 100 patient-years) will also be provided.

Second screening approach

TEAE summary by primary SOC, HLGT, HLT, and PT as well as groupings of events (ie, cataract, neurological events, neurocognitive disorders and "new onset of diabetes" will be provided on the safety population according to baseline LDL-C categories (eg, <70, ≥70 to <90, ≥90 to <110, ≥110 mg/dL).

Hazard ratio (and 95% CI) for alirocumab effect versus placebo within each baseline LDL-C subgroup will be provided using a Cox model with baseline LDL-C (in categories), treatment group and the treatment-by-baseline LDL-C interaction term.

To assess the impact of baseline LDL-C on hazard ratio, a Cox model including the baseline LDL-C (as continuous factor), treatment group and treatment-by-baseline LDL-C interaction term will be used. The p-value from the interaction term will be provided for descriptive purpose to evaluate if there is a potential relationship between baseline LDL-C and hazard ratio.

Second step

For each pre-specified event (cataract, neurological events, neurocognitive disorders, new onset of diabetes) as well as for each event with a potential signal detected in the first step, the time to the first TEAE/event will be compared for patients with 2 consecutive LDL-C <25 mg/dL versus \geq 25 mg/dL, within the alirocumab group, using a Cox model, including the covariate for 2 consecutive LDL-C <25 mg/dL (Yes/No) and prognostic factors of the event analyzed. Adjusted HR (and 95% CI) from this model will be provided.

The list of prognostic factors will be established based on the literature and on study data (as applicable).

Subgroups of patients with treatment-emergent ADA positive response

All TEAEs by primary SOC, HLGT, HLT, and PT as well as local injection site reactions will be described in the alirocumab group according to the following ADA parameters:

- Treatment-emergent ADA positive response (yes/no)
- Persistent/transient/indeterminate treatment-emergent ADA positive response.

Analysis of all treatment-emergent serious adverse event(s)

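### The LDL-C <15 mg/dL safety comparison keeps patients at 15 to <25 mg/dL in its reference group, so its hazard ratio would be diluted if that band also carries risk

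*SAP*

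**What the plan says.** SAP Section 3.4.5.1, in the part on patients with two consecutive LDL-C values below 25 mg/dL, sets out a two-step safety analysis.

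- **Step 1, first approach.** Patients with two consecutive values below 25 are compared with the remainder of their own arm ("ie, patients without 2 consecutive LDL-C <25 mg/dL) within the alirocumab treatment group"). The tables have four columns: placebo, all alirocumab, alirocumab ≥25 and alirocumab <25. The Cox model has a single binary exposure, "including the covariate for 2 consecutive LDL C <25 mg/dL (Yes/No").
- **Step 1, second approach.** Alirocumab is compared with placebo by baseline LDL-C. Achieved LDL-C is not used.
- **Step 2.** For pre-specified events and any signals, the same binary exposure is used with adjustment: ("Yes/No) and prognostic factors of the event analyzed".

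One sentence extends all of this to the lower cut-off: "Similar analyses will be provided considering 15 mg/dL (0.39 mmol/L) as threshold instead of 25 mg/dL". No third category is defined.

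Protocol Section 10.6.3 gives the dose rules that decide who remains in each band. For a patient on 75 mg with two values below 25 but not two below 15, "study treatment with 75 mg Q2W will be continued but additional monitoring with review of individual patient profiles will be implemented". For a patient on 75 mg with two values below 15, "study treatment with 75 mg Q2W will be discontinued at the next visit". Patients on 150 mg with two values below 25 are down-titrated, and the SAP shortens their analysis period "as patients down-titrated from 150 mg to 75 mg are likely to come back above 25 mg/dL".

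**The concern.** When 25 is replaced by 15, the reference becomes every alirocumab patient without two consecutive values below 15. Patients with two consecutive values below 25 but not two below 15 are the exposed group in one analysis and part of the reference in the next. Those kept on 75 mg can spend long periods in that band, and the protocol gives them extra monitoring because its safety is still to be confirmed.

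If the middle band carries some excess risk, the <15 hazard ratio is measured against a reference that already contains part of that risk. The error then runs toward missing a harm, in the LDL-C range where Protocol Section 4 says information is lacking. It would affect both the screening model and the adjusted model. Two overlapping yes/no contrasts also give no direct estimate of a gradient from ≥25 through 15 to <25 down to <15.

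**Working it through.** The plan states no group size, effect size or power for this analysis, so there is no figure of its own to reproduce. The check is how far the split could move the estimate.

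**Definitions**

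- h1: true hazard ratio, middle band versus ≥25.
- h2: true hazard ratio, <15 versus ≥25.
- f: share of the <15 reference group's risk time that comes from middle-band patients.

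All three are assumptions. On f the documents offer only words. The design rationale in Protocol Section 4 expects few patients below 25 in this trial. The benefit-risk conclusion in the same section reports a substantial proportion in earlier studies.

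**Formula.** The reference hazard, relative to ≥25, is (1 − f) + f × h1. Hence

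estimated hazard ratio = h2 / (1 − f + f × h1).

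**Results for h2 = 2.0**

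| h1 | f = 5% | f = 20% | f = 40% |
|---|---|---|---|
| 1.0 | 2.00 | 2.00 | 2.00 |
| 1.25 | 1.98 | 1.90 | 1.82 |
| 1.5 | 1.95 | 1.82 | 1.67 |
| 2.0 | 1.90 | 1.67 | 1.43 |

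For example, h1 = 1.5 and f = 20% gives 2.0 / (0.80 + 0.30) = 2.0 / 1.10 = 1.82.

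**Simulation check.** Cox models were fitted to 9,300 simulated alirocumab patients, 60 replicates per scenario, with h2 = 2.0. The planned split and a <15 versus ≥25 contrast gave, respectively:

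- f = 5%, h1 = 1.5: 1.93 and 1.97.
- f = 21%, h1 = 1.0: 1.91 and 1.91 (no difference; both below 2.0 by simulation error).
- f = 21%, h1 = 1.5: 1.83 and 2.02.
- f = 33%, h1 = 1.5: 1.68 and 1.95.

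These agree with the formula within simulation error.

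**Does the <25 analysis supply the missing contrast?** Its exposed group pools both low bands. Suppose 5% of alirocumab patients are <15 and 20% are in the middle band. The <15 share of the exposed group is then 5/25 = 0.2, and the pooled hazard ratio is approximately 0.2 × 2.0 + 0.8 × h1. That is 1.2 if h1 = 1.0 and 1.6 if h1 = 1.5. Neither is the <15 effect of 2.0.

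**Power, for illustration.** With a two-sided 0.05 test, 9,300 patients, 5% baseline risk, h1 = 1.5 and h2 = 2.0, power is 0.85 under the planned split and 0.92 for <15 versus ≥25 when the shares are 5% and 20%. With shares of 1% and 4% it is 0.31 and 0.32.

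**The case against.** The strongest reply is that the plan already covers the cases that matter. If harm is confined to <15, the planned split is not diluted at all (top row of the table). If both low bands carry the same risk, the <25 analysis shows it against a reference that contains no middle-band patients. The largest losses in the table, such as 2.0 shown as 1.43, belong to that second case. Both points stand. What they leave open is a graded harm, with some risk at 15 to <25 and more below 15. There the <15 analysis dilutes the reference and the <25 analysis dilutes the exposed group.

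Three further points stand as limits on size.

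- The share f is unknown. If few patients go below 25, as the protocol expects, it is small.
- Long residence at 15 to <25 describes only patients kept on 75 mg. Those on 150 mg are down-titrated and expected to rise again.
- The SAP restricts the analysis period only for the below-threshold group, so middle-band patients in the reference also contribute time before their first low value and after any return above 25. If risk follows current LDL-C, the formula overstates the dilution.

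The baseline-LDL-C comparison with placebo does not use this split and is untouched by it. It is indirect, because it cannot attribute an effect to achieved values below 15. Patients <15 are also a subset of those <25, so subtracting one table from the other gives the size of the middle group. Its events would follow only approximately, since the start dates differ, and without a hazard ratio.

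**Conclusion.** The point holds in a conditional form. The reference group for the 15 mg/dL analysis contains the middle band, and no planned analysis contrasts <15 with ≥25. The <15 hazard ratio would be diluted only if 15 to <25 itself carries excess risk.

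For a true hazard ratio of 2.0 and a middle-band hazard ratio of 1.5, the loss is about 2% at f = 5% (1.95), 9% at f = 20% (1.82) and 17% at f = 40% (1.67). These rest on assumed shares and effects and on the excess applying to all middle-band time in the reference.

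A reader might infer that the planned analysis hides any harm of very low LDL-C. The documents do not support that: a harm limited to <15 is not diluted, a harm common to both bands appears in the <25 analysis, and nothing in the protocol or SAP points to a large f. These are exploratory safety comparisons with no alpha or power claim, so this is a modest gap in interpretability and cheap to close.

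**What to change.** In SAP Section 3.4.5.1, add to or replace the repeat at 15 mg/dL with one three-level exposure within the alirocumab group:

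1. two consecutive values <15 mg/dL;
2. two consecutive values <25 mg/dL but never two consecutive <15 mg/dL;
3. neither (reference, the SAP's ≥25 group).

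Use it in the first-approach tables and in both within-alirocumab Cox models (screening and adjusted). Report the hazard ratio of each low level against the common reference. Start each low group's analysis period at the first of its own qualifying values.

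The cost is SAP wording, one recoded covariate and one extra estimate per event. No new data are needed and conduct does not change. The low groups may be small, so some intervals will be wide. The change does not remove the bias from grouping on post-randomization LDL-C, which the SAP itself acknowledges, so the baseline-LDL-C comparison with placebo should stay alongside it.

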### 8.3.2 Lipid parameters

[figure not shown]
Lipid parameter values from blood samples obtained after the randomization visit, run by the central lab, will not be communicated to the sites so that they cannot deduce the treatment group of their patients based on LDL-C level attained. The sponsor's operational team will not have access to lipid parameters after randomization and until after the final database lock has occurred.

For patients who achieve 2 consecutive LDL-C <25 mg/dL (0.65mmol/L) on alirocumab and depending on the dose received, the following will be applied:

- If the dose is 150 mg Q2W:

- If the dose is 75 mg Q2W:

\* **NOTE:** *Additional monitoring includes:*

- *Patient level listing for surveillance and review for patients who are managed by IVRS/IWRS (i.e with planned automatic down-titration from 150 mg to 75 mg, or switch from 75mg to placebo)*
- *Individual patient profile monitoring for potential site alerts for patients on alirocumab 75 mg and not managed by IVRS/IWRS (i.e. with no planned automatic down-titration or switch to placebo by IVRS/IWRS)*

*Further details are provided in [Appendix A](#).*

As described above, in case of LDL-C <25 mg/dL (0.65 mmol/L) on 2 consecutive values and until specific actions are undertaken, patients will be monitored according to process outlined in [Section 10.6.3](#) and [Appendix A](#). In order to maintain the integrity of the blind as much as possible with this monitoring process, the following points will be undertaken:

- Specific steps will be in place to ensure that the work which will be carried out by the central lab group and the communication with the independent external physician(s) (also known as independent physician), who is responsible for closely monitoring patients with these 2 consecutive LDL-C levels, will be in strict confidence.

- The independent physician(s) and the dedicated member of the Phase 3a DMC (implemented for all Phase 3 studies evaluating the efficacy and safety of alirocumab on LDL-C) will work in close collaboration and independently from the clinical team and the sites. This dedicated Phase 3a DMC member will then transmit any information as necessary to the common member involved in both DMCs (CV DMC and Phase 3a DMC)
- The actual LDL-C levels will not be reported to the sites
- Monitoring will be discontinued when specific actions are undertaken as described above, unless patients still display a LDL-C <25 mg/dL

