2.2 STATISTICAL MODIFICATIONS MADE IN THE STATISTICAL ANALYSIS PLAN

The statistical analysis plan history table below gives the timing, rationale, and key details for major changes to the statistical analysis features

- in the first version of the statistical analysis plan dated on 25 January 2016 compared to the protocol amendment 8 (version currently in effect at this time)
- in the amended versions of the statistical analysis plan (versions 2 and 3) compared to the first version of 25 January 2016.

Changes already incorporated in a protocol amendment are listed only in Table 2.

With regard to the study timelines, the first patient was enrolled on 02 November 2012. The first interim analysis occurred in April 2016 with the data cut-off for the interim analysis on 30 November 2015. The second interim analysis occurred when approximately 1210 patients had at least one positively-adjudicated primary efficacy endpoint, with review of the data by the DMC in November 2016.

SAP			
version	Date		
number	approved	Rationale	Description of statistical changes
1	25-Jan-2016	Imputation method not planned for missing lipid values	For patients without lipid values in the time window analyzed, multiple imputation will be used with different imputation strategies depending on the time of those missing values (during the treatment period or after treatment discontinuation) (see Section 3.4.7.4.1)
1	25-Jan-2016	End of analysis period for the analysis of TEAEs for patients with 2 consecutives low LDL-C did not take into account down-titrations from 150 mg to 75 mg	In the specific analysis of TEAEs for the subgroup of patients with two consecutive LDL-C <25 mg/dL (respectively 15 mg/dL) within the alirocumab treatment group, the upper limit of the analysis period for patients down-titrated from 150 mg to 75 mg will end at the date of last injection of 150 mg +70 days (see Section 3.4.5.1).
1	25-Jan-2016	Selection of patients with 2 consecutive LDL-C <25 mg/dL (respectively 15 mg/dL) modified consistently with the other studies of the program.	The patients will be considered as having 2 consecutive LDL-C <25 mg/dL (respectively 15 mg/dL) if these values are spaced out by at least 21 days (see Section 3.1.5.4).

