3.1.4 Safety endpoints

Following injections are considered as double-blind IMP injections:

• For patients randomized in the placebo group: any injection from double-blind kits;

• For patients randomized in the alirocumab group: any injection from double-blind kits excepted placebo injections given to maintain the blind in case of 2 consecutive LDL-C values <15 mg/dL.

Of note potential additional training injections after randomization using training injection kits will not be taken into account.

The period of safety observation starts from the time when the patient gives informed consent and is divided into three periods:

- PRE-TREATMENT period: defined from the signed informed consent up to the first dose of double-blind IMP injection;
- Treatment-emergent adverse event (TEAE) period: defined as the time from the first dose of double-blind IMP injection to the last dose of double-blind IMP injection +70 days (10 weeks), (as residual effect of treatment is expected until 10 weeks after the stop of double-blind IMP).

The TEAE period will include:

- The TREATMENT period defined as the time from the first dose of double-blind IMP up to the day of last dose of double-blind IMP injection +21 days, as serum concentration of alirocumab >10 μ g/mL is expected for approximately 21 days following administration of 150 mg, and because throughout the previous studies it was observed that when alirocumab concentrations declined below this concentration, decrease in effect on LDL-C is observed.
- The RESIDUAL TREATMENT defined as the time from the day of last dose of double-blind IMP injection +22 days up to the day of last dose of double-blind IMP injection +70 days (10 weeks).
- POST-TREATMENT period: defined as the time starting the day after the end of the TEAE period.

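### The low-LDL-C safety window closes 70 days after the last 150 mg injection for every down-titrated patient, even when LDL-C stays or again becomes low on 75 mg

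*SAP*

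**What the plan says.** SAP 3.4.5.1 compares, within the alirocumab arm, patients with and without two consecutive LDL-C values below 25 mg/dL. For patients with such a pair, the analysis runs over "the period starting from the first of the 2 consecutive LDL-C lower than 25 mg/dL to the upper limit of the TEAE period". Patients moved from 150 to 75 mg are the exception, "for whom the analysis period will end at the date of last injection of 150 mg +70 days". The reason given is a general expectation: "as patients down-titrated from 150 mg to 75 mg are likely to come back above 25 mg/dL". No condition on LDL-C after the dose change is attached.

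The section adds: "Similar analyses will be provided considering 15 mg/dL (0.39 mmol/L) as threshold instead of 25 mg/dL". SAP 2.2 confirms that the same cut was meant for both thresholds, since it names the subgroup with "two consecutive LDL-C <25 mg/dL (respectively 15 mg/dL) within the alirocumab treatment group". SAP 3.4.5.3 reuses the window for PCSA summaries.

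Protocol 10.6.3 sets down-titration in motion after two values below 25 mg/dL on 150 mg. It then keeps the patient on 75 mg "for the remaining duration of the study, unless patient meets criteria below". Those criteria cover two values below 25 mg/dL on 75 mg (treatment continues, with added monitoring) and two values below 15 mg/dL on 75 mg (blinded switch to placebo). Protocol 8.3.2 says: "Monitoring will be discontinued when specific actions are undertaken as described above, unless patients still display a LDL-C <25 mg/dL".

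**The concern.** The cut rests on what is likely for the group and is applied to every member of it. Two patients on the same dose with the same LDL-C can therefore be handled differently. One who was always on 75 mg is followed to the end of the TEAE period. One who reached 75 mg by down-titration is cut off 70 days after the last 150 mg injection. Both carry the same Yes value in the Cox model.

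The patients who lose follow-up are those whose LDL-C remains very low despite the lower dose, and they carry the most information on long exposure to low LDL-C. The pre-specified events are cataract, neurological events, neurocognitive disorders and new-onset diabetes, and slow-onset events are the most exposed to early truncation. At the 15 mg/dL threshold the rule can also place the end of the period before its start, and the SAP does not say what happens then.

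**Working it through.** The plan states no figure for this window, so there is none to reproduce. The check is date arithmetic on the documents' own rules.

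**Inputs**
- Start: first value of the qualifying pair. End: last 150 mg injection + 70 days if down-titrated, otherwise the end of the TEAE period, which is last double-blind injection + 70 days (SAP 3.1.4, 3.4.5.1).
- Lipid visits after Month 2: M4, then every 4 months to M24, then every 6 months (Protocol 1.2.1). Down-titration takes place at the visit after the second low value (10.6.3).
- Up-titration is at Month 2, so M4 is normally the earliest LDL-C on 150 mg.
- One month is 30.4375 days, so 70 days is 2.30 months.
- Assumptions: last 150 mg injection at the down-titration visit; LDL-C below 25 mg/dL throughout; treatment to month T.

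**Share of low-LDL-C time dropped**

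With first low value at month S and down-titration at month D, the full period is T + 2.30 − S and the counted period is D + 2.30 − S. The dropped share is (T − D)/(T + 2.30 − S).

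Example: S = 4, D = 12, T = 36. Counted: (365.25 + 70) − 121.75 = 313.5 days. Full: (1,095.75 + 70) − 121.75 = 1,044 days. Dropped: 730.5/1,044 = 70%.

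| S, D | T = 24 | T = 36 | T = 40 | T = 64 |
|---|---|---|---|---|
| M4, M12 | 54% | 70% | 73% | 84% |
| M12, M20 | 28% | 61% | 66% | 81% |
| M20, M30 | – | 33% | 45% | 73% |
| M24, M36 | – | – | 22% | 66% |

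A last 150 mg injection 14 days before the visit changes the first row only slightly (56% at T = 24, 74% at T = 40).

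Follow-up can also be projected from the protocol's enrolment table. Its monthly rates sum to 2,564 + 28 × 560 = 18,244, against the stated 18,000, and with a 64-month study they give a mean follow-up of about 40.4 months. Over that accrual the dropped person-time is 73% (first low at M4), 66% (M12), 52% (M20) and 42% (M24).

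**Length of the period at 15 mg/dL**

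Down-titration is triggered below 25 mg/dL, so a pair below 15 mg/dL can first arise on 75 mg. If its first value falls at the next regular visit, the length is 70 days minus the visit interval:
- 4-month interval: 70 − 122 = −52 days
- 6-month interval: 70 − 183 = −113 days
- both ±14-day visit windows at their limits: 70 − 94 = −24 and 70 − 155 = −85 days

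Example: 20 mg/dL at M4 and M8 on 150 mg, 75 mg from M12, below 15 mg/dL at M16 and M20. The period starts on day 487 and ends on day 435.

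At 25 mg/dL the triggering pair normally precedes the dose change, so the length is positive. The exception is a triggering pair less than 21 days apart, which SAP 3.1.5.4 does not count, followed by a qualifying pair on 75 mg.

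**The case against.** The cut was a deliberate choice, recorded with a reason in SAP 2.2, and 70 days matches the residual-effect period in SAP 3.1.4. Counting years on 75 mg after LDL-C has recovered would dilute the low-LDL-C group. That argument stands for patients who recover. It does not cover those who do not.

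Several stronger readings are tempting and are not supported:
- *The rule drops most of the low-LDL-C time of down-titrated patients.* A patient who soon returns above 25 mg/dL loses little or none. The losses above apply to patients who stay low, and the documents do not say how many there are.
- *The protocol contradicts the SAP.* Providing for patients who stay low on 75 mg is compatible with expecting most to recover.
- *No scheduled LDL-C on 75 mg can fall inside the 70 days.* This is true of the regular visits. The final visit follows a common calendar date and the early end-of-treatment visit follows discontinuation. Both collect lipids, and either may fall inside.
- *The trial's assessment of harm is compromised.* The Tier 1 comparisons between arms and the comparison by baseline LDL-C do not use this cut. The SAP itself warns that the within-alirocumab comparison is open to bias.
- *Event rates are mechanically lowered.* Events and person-time are removed together, and neither moves to the comparator. What is lost is information on long exposure.

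The negative-length case needs a patient without a pair below 15 mg/dL on 150 mg who then has one on half the dose, which is probably uncommon.

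**Conclusion.** The concern holds in a limited form. The window ignores LDL-C on 75 mg and excludes all later low-LDL-C follow-up of down-titrated patients who stay or again become low. In the scenarios shown this is about 22% to 84% of that time. Under the planned accrual it exceeds half when the first low value comes at about M20 or earlier. These shares assume LDL-C stays low and treatment continues to the end of follow-up; they illustrate individual schedules and do not estimate the effect on the trial.

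At 15 mg/dL the rule gives a start after the end for a pair first met at a regular visit on 75 mg, so as written it fails for those patients. The number affected cannot be obtained from the documents. The consequences stay within the within-alirocumab low-LDL-C comparison and the PCSA summaries that borrow its window.

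**What to change.** In SAP 3.4.5.1, keep the +70-day cut for a qualifying pair that occurred on 150 mg. Add that if a down-titrated patient has two consecutive values, at least 21 days apart, below the threshold (25, respectively 15 mg/dL) on 75 mg, time from the first of those values to the end of the TEAE period is also counted, as for any other patient on 75 mg. Patients without such a pair, including those with no later LDL-C, keep the current cut, so nobody is assumed low without evidence. Report the current unconditional window as a sensitivity analysis, and apply the same definition to the PCSA summaries in 3.4.5.3.

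In the M4/M12/M36 example with low values at M16 and M20, counted time becomes 313.5 + (1,165.75 − 487) = 992.25 of 1,044 days, so the loss falls from 70% to 5%. In the 15 mg/dL example, with the switch to placebo at M24, the period becomes about (730.5 + 70) − 487 = 313.5 days instead of −52.

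The cost is SAP wording, a short programming change (a patient may contribute two separate intervals) and one more sensitivity table. LDL-C values and dose dates are already collected. This concerns the analysis window only and implies no change to dosing.
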